## **4. STATISTICAL METHODS**

### **4.1. General Methods**

All outputs will be incorporated into Rich Text Format (RTF) files, sorted, and labeled according to the International Council for Harmonisation of Technical Requirements for Pharmaceuticals for Human Use (ICH) recommendations, and formatted to the appropriate page size(s).

Tabulations will be produced for appropriate demographic, Screening, Baseline, efficacy, and safety parameters. For categorical variables, summary tabulations of the number and percentage within each category (with a category for missing data) of the parameter will be presented. For continuous variables, the mean, median, lower quartile (Q1), upper quartile (Q3), standard deviation, minimum and maximum values will be presented. Time-to-event data will be summarized using Kaplan-Meier Methodology using 25th, 50th (median), and 75th percentiles (if available) with associated two-sided 95% confidence intervals (Hall-Wellner Bands), as well as percent of censored observations.

Formal statistical hypothesis testing will be performed on the primary and secondary efficacy endpoints with all tests conducted at the two-sided, 0.05 level of significance.

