#### **4.4. Withdrawals, Dropouts, Loss to Follow-up**

Subjects who withdraw from the study were not to be replaced.

For subjects who cease taking study drug but who wish to continue in the study, the planned schedule of assessments should be followed, except for the collection of blood samples for MT concentrations (with protocol version 7.0 and 7.0 UK). These subjects will be classified as “the off-treatment-on-study” (TOTOS) group. A subgroup of TOTOS are the subjects with antidementia therapy initiation (AchEI and/or memantine) after informed consent.

Interruption of dosing for up to a maximum of 14 consecutive days may be allowed if the Investigator determines this is indicated (e.g., due to an AE or any other reported change in the subject’s physical condition in the judgment of the Investigator) on a maximum of two occasions. If this is exceeded, study drug would need to be discontinued; however, the subject will be encouraged to continue study participation off-treatment (TOTOS). If subjects stopped the dosing without the Investigator’s approval, they could get back on treatment.

For each subject who withdraws from the study, the decision will be made as part of the BDRM if the withdrawal is potentially treatment-related. For potentially treatment-related dropouts, the fraction of subjects who withdrew at a given time point will be calculated for each treatment group. In addition, a table and figure of the Kaplan-Meier estimator of time to potential treatment-related withdrawal will be given.

Sponsor:	TauRx Therapeutics Ltd.		
Protocol:	TRx-237-039		
Document Version No.:	3.0	Document Date:	07-JUN-2023

---

A separate listing of the subjects with antidementia therapy initiation will be provided, including the reason if available. Furthermore, listings will be provided for the efficacy endpoints showing all assessments and assessments which are impacted by antidementia therapy initiation being flagged.

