### 5.3. Sample Size Justification

Sample size estimations to achieve 90% power (two-sided alpha = 0.05) to detect a difference between HMTM 16 mg/day and true placebo have been performed for the two co-primary clinical endpoints. These assume a withdrawal rate of 20% to 25% over 52 weeks. The study sample size – here restricted to subjects randomized under protocol version 5.0 or higher as this is the primary analysis population – of approximately 450 subjects (approximately 200 subjects in each treatment group, with a further 50 subjects for secondary analyses of an HMTM 8 mg/day group) is based on the ADCS-ADL23 as a larger sample size is required to achieve the target power.

Based on an estimated decline in ADCS-ADL23 over 52 weeks in the control arm of 7.7 units with an estimated SD of 8.5 units, the study will have approximately 93.2% power (two-sided alpha=0.05) to detect a reduction in decline of 3.4 units or more. The 3.4 units are motivated by an estimated treatment effect of  $5.0 \pm 1.6$  (mean  $\pm$  standard error) units in the pooled studies TRx-237-005/ TRx-237-015.

Based on an estimated decline in ADAS-cog11 over 52 weeks based on pooled information from Studies TRx-237-005 / TRx-237-015 in the control arm of 6.5 units with an estimated SD of 5.9 units, 200 subjects per treatment arm provide approximately 96.7% power (two-sided alpha=0.05) to detect a reduction in decline of 2.6 units or more. The 2.6 units represent a conservative value as the estimated treatment effect based on pooled Studies TRx-237-005 / TRx-237-015 is  $5.2 \pm 1.3$  (mean  $\pm$  standard error) units.

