#### 5.9.5. Time-to-event/Decline Analysis (Sensitivity)

This analysis, based on the ITTv5 population, will include off-treatment measurements (TOTOS) and will be done separately for the primary and secondary efficacy variables ADAS-cog11, ADCS-ADL23, and MRI whole brain volume. It will only compare subjects on HMTM 16 mg/day and control.

Time-to-event/decline will be calculated as date of onset of decline – date of first dose + 1 and will use only data from the double-blind treatment phase and upscaled values for the two co-primary endpoints.

Time of onset of decline is the first of two consecutive measurements with worsening, whereas worsening is defined as an impairment, with respect to the Baseline value of at least a change in units as outlined here:

- ADAS-cog11, ADCS-ADL23: 1
- MRI whole brain volume: 6,500 (mm^3 =  $\mu$ L)

If the threshold of the MRI whole brain volume does not appear to be reasonable once the unblinded randomization codes are used, these can be modified slightly (similarly if a model may not converge).

If the available Week 52 value (or the value of the last assessment in general, in case of early termination) is worsened without a prior worsening, an onset of decline will be triggered at Week 52 (or the respective last visit) for that subject. Subjects without any decline will be censored at the date

Sponsor:	TauRx Therapeutics Ltd.		
Protocol:	TRx-237-039		
Document Version No.:	3.0	Document Date:	07-JUN-2023

of last assessment, but if a subject missed the scheduled visit, the subject is censored at the target day of the scheduled visit.

Any missing efficacy/imaging value for a scheduled visit will be treated as a worsening from baseline, for that visit, but a single missing value at the last planned visit without a missing value or without a worsening in the previous visit will not count as a decline. If the time of onset is missing due to a missed scheduled visit the scheduled date of the missing visit will be used.

The Cox proportional hazards model with effects for treatment group and the randomization stratification variables will be used to compare HMTM 16 mg/day versus control by way of Hazard Ratio, 95% confidence interval, and p-value. A graph and a table of the Kaplan-Meier estimates will be provided.

Sample SAS code (will be fully validated at the analysis stage):

```
PROC PHREG DATA=dataset PLOTS(OVERLAY)=SURVIVAL;  

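### SAP 4.1 labels simultaneous Hall-Wellner bands as the 95% confidence intervals of single Kaplan-Meier percentiles, so those descriptive intervals are conservative

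*SAP*

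**What the plan says.** SAP Section 4.1 (General Methods) sets the general rule: "Time-to-event data will be summarized using Kaplan-Meier Methodology using 25"th, 50th and 75th percentiles where available, with "associated two-sided 95% confidence intervals (Hall-Wellner Bands"). The parenthesis follows the interval and names the method for it. The sentence does not mention a plotted curve.

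No other section names an interval method for a Kaplan-Meier percentile:

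- SAP 5.9.5 (time to decline on ADAS-cog11, ADCS-ADL23 and MRI whole brain volume) says "A graph and a table of the Kaplan-Meier estimates will be provided". Treatments are compared by a Cox model, "by way of Hazard Ratio, 95% confidence interval, and p-value".
- The sample code in 5.9.5, "PROC PHREG DATA=dataset PLOTS(OVERLAY)=SURVIVAL", requests a survival plot and sets no interval type, transformation or band range.
- SAP 4.4 plans "a table and figure of the Kaplan-Meier estimator of time to potential treatment-related withdrawal", again without an interval method.
- SAP 5.12.2 refers time to first TEAE to the model in 5.9.5.
- Protocol 17.4.9 asks for Kaplan-Meier summaries and says nothing about percentile intervals.

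**The concern.** A 95% interval for a median should contain the true median in 95% of repetitions. A 95% Hall-Wellner band answers a different question: whether the entire curve lies inside the band. To do that it must be wider at each single point than a pointwise limit, so inverting it at one percentile gives an interval that is too wide for its label.

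A reader of the tables would take the tabulated 95% at face value and see more uncertainty than the data carry. A wider upper limit also fails to cross the percentile more often, so more upper limits would be reported as not estimable. The programmer would have to either follow the SAP and table mislabelled intervals, or use pointwise limits and depart from the SAP.

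**Working it through.** **Figure in the plan.** The stated level is 95%, two-sided. Pointwise limits reproduce it approximately: in simulations with 200 subjects (the SAP 5.3 arm size, "approximately 200 subjects in each treatment group"), exponential event times and linear or log-log limits, they covered each percentile in 93.4% to 96.4% of runs. Hall-Wellner limits do not.

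**Formulas.** Let S be the Kaplan-Meier estimate, σ² the Greenwood sum, and a = nσ²/(1 + nσ²). Without censoring, a is the proportion with events by time t.

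- Pointwise half-width: 1.96·σ·S
- Linear Hall-Wellner half-width: c·n^(-1/2)·(1 + nσ²)·S, where c is the 95% point of the largest absolute value of a Brownian bridge on [0, aU], and aU is the value of a where the band ends
- Ratio: c / (1.96·√(a(1−a)))
- Coverage at one point: 2Φ(c/√(a(1−a))) − 1

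**Full-range band, c = 1.358.**

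- Median: 1.358/(1.96 × 0.5) = 1.386; 1.358/0.5 = 2.716, so coverage is 99.3%.
- 25th and 75th percentiles: √(0.25 × 0.75) = 0.433; 1.358/(1.96 × 0.433) = 1.600; 1.358/0.433 = 3.136, so coverage is 99.8%.

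**Dependence on where the band ends.** The documents do not give this, so it is shown as a range.

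| aU | c | Ratio at 25th (coverage) | Ratio at median (coverage) |
|---|---|---|---|
| 0.80 | 1.357 | 1.60 (99.8%) | 1.38 (99.3%) |
| 0.50 | 1.273 | 1.50 (99.7%) | 1.30 (98.9%) |
| 0.40 | 1.198 | 1.41 (99.4%) | not reached |
| 0.30 | 1.087 | 1.28 (98.8%) | not reached |
| 0.25 | 1.014 | 1.20 (98.1%) | not reached |

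**Likely event fraction for time to decline.** A worsening of 1 unit at Week 52 is enough to trigger decline (SAP 5.9.5). The inputs are the planning values in SAP 5.3: control declines of 6.5 (SD 5.9) and 7.7 (SD 8.5), with reductions of 2.6 and 3.4. Changes are assumed normal with the same SD in both arms.

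- ADAS-cog11: control Φ((6.5−1)/5.9) = 82%; treated Φ((3.9−1)/5.9) = 69%.
- ADCS-ADL23: control Φ((7.7−1)/8.5) = 78%; treated Φ((4.3−1)/8.5) = 65%.

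On the co-primary scales events should therefore be common, which is the upper part of the table.

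**Simulation with continuous times** (200 subjects, linear limits, 2,000 runs). Hall-Wellner coverage was 99.3% to 99.9%, against 93.4% to 94.9% pointwise. With 22.5% dropout and 80% events, the median width ratio on the time scale was 1.41 at the median and 1.59 at the 25th percentile.

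**Visit-based times.** Decline can be dated only around Weeks 13, 26, 39 and 52, and SAP 5.9.5 plans both a visit-window version and an actual-date version. The event patterns here are assumptions; the documents give none.

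- With 200 subjects, about 75% events and 20% dropout, the pointwise and Hall-Wellner intervals were identical in about 80% to 87% of runs of the visit-window version. With dates spread within 14 days of the visits, the ratio was about 1.2 to 1.4.
- Over four other patterns (15% dropout), identity in the visit-window version ranged from 9% to 100% of runs, depending on pattern and percentile. The pointwise interval itself covered 97% to 100%.

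**The case against.** The strongest reply is that the 1.4 to 1.6 ratio belongs to continuous event times, while the main use is tied to four visits. That stands. In the visit-window version limits can fall only on the visit days, so the choice of method often changes nothing, and pointwise limits do not bring coverage back to exactly 95%. The actual-date ratio depends on where a percentile falls relative to the visits, so no single factor can be quoted for it.

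A reader might infer that every Kaplan-Meier quartile interval in the trial is 1.4 to 1.6 times too wide. The documents do not support that:

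- For treatment-related withdrawal, SAP 5.3 assumes 20% to 25% total withdrawal, of which only part counts as events. The 25th percentile would barely be reached and the higher ones not at all, so there is little or no interval to widen.
- For time to first TEAE, SAP 5.12.2 points to the model in 5.9.5 and does not itself ask for percentile intervals.
- No transformation or band range is stated. A log-log band inverted naively gave larger ratios, about 2.5 or more with 200 subjects, so the factor could also be higher.

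A reader might also infer that efficacy conclusions are at risk. They are not. Section 5.9.5 is a sensitivity analysis that compares treatments by Cox hazard ratio, and the co-primary analyses use a mixed model. The error widens intervals and cannot produce a false positive.

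The parenthesis may have been meant for plotted curves. That is plausible, but the sentence does not say so, and that reading would need the same correction.

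**Conclusion.** The point holds as a mislabelled descriptive interval. As written, SAP 4.1 gives each Kaplan-Meier percentile a conservative interval under a 95% label. The size is about 1.4 times (median) to 1.6 times (quartiles) the pointwise width, with 99.3% to 99.8% coverage. That assumes continuous event times and a linear band over most of the event range. At the 25th percentile it falls to about 1.2 to 1.3 times, with 98% to 99% coverage, when only 25% to 30% have events. For time to decline, the main place where it matters, the excess is generally smaller and often nil in the visit-window version, under event patterns that had to be assumed. No hypothesis test, hazard ratio or co-primary estimate changes. It is worth correcting because the rule is wrong as written and the correction is short.

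**What to change.** In SAP 4.1, specify pointwise 95% confidence intervals for the Kaplan-Meier percentiles, for example Brookmeyer-Crowley with a stated transformation. Other pointwise methods are acceptable if named. If Hall-Wellner bands are wanted, reserve them for the plotted curves, label them as simultaneous, and state their transformation and time range.

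The cost is one phrase and possibly a rerun of the affected tables. It is not entirely free: SAP Section 10 records that version 3.0 followed the data snapshot of 28 April 2022 and the partial unblinding. The change should therefore be recorded as made after unblinding of the double-blind phase, and the study report should state which intervals were tabulated.

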### **4.2. Data Conventions**

Mean, median, standard deviation, standard error, Q1 and Q3 will be presented with one more decimal place compared to the raw data, and minimum and maximum will be presented with the same number of decimal places as the raw data. Percentages will be presented with one decimal place.

Wherever a calendar date is presented in a listing, the corresponding Study Day will be included, with Study Day defined as:

- date – first dose date + 1, where date >= first dose date
- date – first dose date, where date < first dose date

For listings including day 1 data with assessments collected prior to and after first study drug, a flag will be included for pre-dose assessments.

The following conversion factors will be used to convert days to months or years where applicable:

- 1 month = 30.4375 days
- 1 year = 365.25 days
- 1 week = 7 days

Additional data handling rules are as follows:

Sponsor:	TauRx Therapeutics Ltd.		
Protocol:	TRx-237-039		
Document Version No.:	3.0	Document Date:	07-JUN-2023

- Age (years) = year of informed consent – year of birth
- Weight values recorded in pounds will be converted to kilograms using the following formula:  
kilograms = pounds/2.2046
- Height values recorded in inches will be converted to centimeters using the following formula:  
centimeters = inches\*2.54
- Temperature recorded in Fahrenheit to Celsius:  $1^{\circ}\text{C} = (\text{°F} - 32)/1.8$
- Duration on study (weeks) = (Last visit date – randomization date + 1) / 7
- Duration on treatment (weeks) = (Last dose date – first dose date + 1) / 7
- (Absolute) Change from Baseline = Value at the time point – Baseline value
- Relative Change from Baseline = (Value at the time point – Baseline value) / Baseline value \* 100

To calculate descriptive / inferential statistics for laboratory values containing values below/above the limit of quantification, the following general rule of thumb will be applied: each laboratory value below/above the limit of quantification will be imputed numerically to the nearest value below/above the limit, respecting the same number of decimal places than numerical values (e.g., if the number of decimal places=0, subtract/add 1 to the limit of quantification (LOQ); if the number of decimal places=1, subtract/add 0.1 to the LOQ, etc.). Is the LOQ already the lowest value larger than zero, the LOQ will be imputed numerically to the nearest value below the limit with one more decimal place (e.g., if the LOQ is 1, subtract 0.1 from the LOQ: 0.9). The subject data listings will not show the imputed value, but that the value is below or above the limit of quantification.

Partial dates will be reviewed and imputed (where possible) after the BDRM and before unblinding, potentially resulting in an Excel file, which will be provided to Cytel for the use in the analysis. Remaining cases (if existing), which are required for calculation, or cases for which no additional information is provided after the BDRM or if no file has been generated will be handled as follows:

#### Start dates

- For missing start day only: Day will be imputed as the first day of the month (i.e., 1) with the following exception: if the partial date falls in the same month and year as the first date of dosing, then the partial date will be imputed to equal the first date of dosing (unless the known end date lies before the first date of dosing, when imputing the incomplete start date).
- For missing start day and month: Day and month will be imputed as the first day of the year (i.e., 1 January) with the following exception: if the partial date falls in the same year as the first date of dosing, then the partial date will be imputed to equal the first date of dosing (unless the known end date lies before the first date of dosing, when imputing the incomplete start date).

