#### 5.12. Safety Analyses

Safety analyses will be conducted using the Safety population. Key analyses will be repeated based on the Safetyv5 population. The analyses of the double-blind treatment phase are limited to the events up to the first dose of the open-label treatment phase. The eye exam is assigned to the double-blind treatment phase, if it was performed until the end of the Week 52 protocol-specified visit window.

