#### 6.13.2. Adverse Events

Adverse events (AEs) will be coded using the MedDRA version 20.1 and are displayed in tables and listings using SOC and Preferred Term (PT).

TEAEs during the open-label treatment phase are defined as AEs with:

- Onset after first dose of study drug of the open-label treatment phase or
- Worsen in intensity after first dose of study drug of the open-label treatment phase or
- Worsen in treatment relationship after first dose of study drug of the open-label treatment phase.

The total number of subjects and the numbers stratified by MedDRA SOC and PT, along with the corresponding percentage, will be derived and summarized by the original randomized treatment group from the double-blind treatment phase (MTC 8 mg/week, HMTM 8 mg/day, HMTM 16 mg/day), the pooled HMTM group (HMTM 8 mg/day + HMTM 16 mg/day), and overall, for the following events:

- Any TEAE
- Any TEAE with an onset on the first day of the open-label treatment phase after the first dose of the open-label treatment phase, complemented by a subject data listing
- Any TEAE (categorized by severity)
- Any TEAEs assessed by the Investigator as related to treatment (i.e., related or possibly related)
- Any TEAEs severe in intensity and assessed by the Investigator as related to treatment (as defined above)

Sponsor:	TauRx Therapeutics Ltd.		
Protocol:	TRx-237-039		
Document Version No.:	3.0	Document Date:	07-JUN-2023

---

- Any TEAE that resulted in interruption or discontinuation of study drug (presented separately and combined)
- Any serious adverse event (SAE)
- Any serious adverse reaction (SAR), which are the SAEs judged to be possibly related or related to the study drug by the Investigator
- Malignancies other than non-melanoma skin cancers
- *TauRx AE Groupings:* Subsets of TEAEs (defined by PT), summarized per grouping and sub-grouping (see Section 5.12.2).
- The protocol-specified AEs of special interest (AESI), which are hemolytic anemia and lens discoloration. A list of all identified events will be provided to the Statistical Programming team.

In addition, separate summaries of AEs by MedDRA SOC and PT will be provided for:

- Post-treatment TEAEs (after the open-label treatment phase)

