### **HMTM Treatment Phase**

For the Safety-HMTM population (see Section 3.1.3), AEs of/ during the HMTM treatment will be analyzed. This means, that for subjects originally randomized to control, events of/ during the double-blind treatment phase (before the first dose of HMTM treatment during the open-label treatment phase) are excluded from this analysis.

The total number of subjects and the numbers stratified by MedDRA SOC and PT, along with the corresponding percentage, will be derived and summarized by the original randomized treatment group from the double-blind treatment phase (MTC 8 mg/week, HMTM 8 mg/day, HMTM 16 mg/day), the pooled HMTM group (HMTM 8 mg/day + HMTM 16 mg/day), and overall, for the following events:

- Any TEAE
- Any TEAE (categorized by severity)
- Any TEAEs assessed by the Investigator as related to treatment (i.e., related or possibly related)

Sponsor:	TauRx Therapeutics Ltd.		
Protocol:	TRx-237-039		
Document Version No.:	3.0	Document Date:	07-JUN-2023

- Any TEAEs severe in intensity and assessed by the Investigator as related to treatment (as defined above)
- Any TEAE that resulted in interruption or discontinuation of study drug (presented separately and combined)
- Any serious adverse event (SAE)
- Any serious adverse reaction (SAR), which are the SAEs judged to be possibly related or related to the study drug by the Investigator
- Malignancies other than non-melanoma skin cancers

For additional more general information regarding AEs, please see Section 5.12.2.

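### The partial-date rule for adverse events is anchored only to the first study dose, so an unresolved start date in the open-label switch month is placed before HMTM exposure in late starters

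*SAP*

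**What the plan says.** SAP 4.2 (Data Conventions) handles partial dates in two steps.

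- **Manual review.** "Partial dates will be reviewed and imputed (where possible) after the BDRM and before unblinding". Here BDRM is the blinded data review meeting for the double-blind phase.
- **Fallback rule.** It covers what the manual review leaves open: "Remaining cases (if existing), which are required for calculation". For a start date with only the day missing, "Day will be imputed as the first day of the month (i.e., 1) with the following exception": the first dose date is used "if the partial date falls in the same month and year as the first date of dosing", unless a known end date lies before it. With day and month missing, the default is 1 January, and the same exception applies to the year of first dosing.

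Section 4.2 takes its first dose as a single study-level date. Study Day, for example, is "date – first dose date + 1, where date >= first dose date".

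Three later passages decide which table an event enters:

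- SAP 5.12: "The analyses of the double-blind treatment phase are limited to the events up to the first dose of the open-label treatment phase".
- SAP 6.13.2, first route to an open-label treatment-emergent event: "Onset after first dose of study drug of the open-label treatment phase or". The other two routes are worsening in intensity and worsening in treatment relationship after that dose.
- SAP 6.13.2, HMTM Treatment Phase: for subjects randomized to control, events dated "before the first dose of HMTM treatment during the open-label treatment phase) are excluded from this analysis".

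Section 6 gives no partial-date rule for adverse events. For medications, SAP 6.9 carries over the Section 5.8 convention, under which undeterminable timing counts as concomitant.

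**The concern.** At first dosing the rule leans towards the drug's risk: when the month is known and matches, an event of uncertain day is treated as starting on treatment. At the switch the same uncertainty is resolved the other way, because the default (the 1st) falls before the first open-label dose.

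For subjects randomized to control, that dose is their first HMTM, at 16 mg/day. An event that began just after it but is dated only to the month would leave the open-label and HMTM-phase safety tables and be dated to the control period. The window matters to the plan itself. The UK protocol version makes the first open-label follow-up an in-clinic visit because some subjects are then receiving HMTM for the first time (SAP 1.4), and SAP 6.13.2 plans a table of events starting on the first open-label day.

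**Working it through.** The plan states no figure on this point, so there is none to reproduce. The check applies the rule as written and then counts.

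**1. Can the existing exception reach the switch month?** The Week 52 protocol window is study day 351 to 379 (SAP Table 5). Taking 365 first-dose dates and an open-label start 364 days later, give or take 14 days, gives 365 × 29 = 10,585 combinations. In none do the two doses share a month and year, so the day-missing exception never applies at the switch.

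**2. Worked example.** First dose 14 September 2020; first open-label dose 364 days later, 13 September 2021 (study day 365); event start recorded only as September 2021.

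- Rule as written: 1 September 2021, study day 353, which is 365 − 353 = 12 days before the first open-label dose. In a control subject it is dated to the control period.
- With the first open-label dose as a second anchor: 13 September 2021, counted under HMTM.

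**3. Month also missing.** The same subject with an event dated only 2021 goes to 1 January 2021. If the switch falls in the same calendar year as first dosing, the event goes to the first double-blind dose. Both dates normally precede HMTM in a late starter.

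**4. Share of first-month events exposed.** Assumptions, not in the documents: open-label start day d uniform on 1 to 30, and onset uniform over the 30 days from that dose.

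- Same calendar month as the dose: Σ(31 − d)/(30 × 30) = 465/900 = 0.517.
- Less starts on the 1st, where the rule does no harm: 30/900 = 0.033.
- Remainder: 435/900 = 0.483, about 48%.

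**5. Among unresolved partial dates in the switch month.** Assumption: true onset uniform over that month, on the real calendar from step 1.

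| Quantity | Share |
|---|---|
| Placed before the open-label dose by the rule | 96.7% |
| True onset on or after the dose | 51.6% |
| True onset on or after the dose, yet placed before it | 48.4% |
| Misplaced, as a share of those truly on or after (0.484/0.516) | about 94% |
| With the second anchor: true onset before the dose, placed under HMTM | 48.4% |

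**6. Scale.** The share of start days left missing and unresolved is not given. For 2%, 5% or 10% (assumed), 0.483 × share = 1.0%, 2.4% or 4.8% of late starters' first-month open-label events. If events were even over 52 weeks (also assumed), multiplying by 30/364 gives about 0.08% to 0.4% of their open-label events.

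**The case against.** The strongest reply is that the manual review comes first. Under SAP 1.5 the double-blind phase ends with the last subject's Week 52 visit, so most subjects had already switched by then. Their switch-month events must be placed before or after the open-label dose for the double-blind analysis itself. A reader might infer that a review before unblinding cannot touch open-label events; the documents do not support that, and the review could settle many of these dates. It cannot settle events reported later. The snapshot is dated 28 April 2022 (SAP 10), and the open-label data review meeting is described only as producing a population tracker (SAP 3.1.1). SAP 6.13 also sets new adverse event information aside when it asks for changed double-blind data to be investigated.

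A second reply is that the anchor is ambiguous: SAP 6.13.1 uses an unqualified first dose date that must mean the open-label one, so a programmer might apply the Section 4.2 rule by phase. That is possible, but Section 4.2 defines its Study Day from one date, and 6.13.2 names the open-label dose when it means it. At best the text needs clarifying.

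Third, conduct limits the frequency. Adverse events are reviewed before and after dosing at Visit 7 and again four weeks later (Protocol Table 10-3), the start date is a recorded item (Protocol 16.2), and serious events are reported within 24 hours (Protocol 16.7). This stands, and it is why the count is probably small. Incidence rates are also not formally tested (SAP 5.12.2).

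**Conclusion.** The gap is real and runs one way for late starters. As written, an unresolved partial start date in the switch month goes to the 1st, before the first open-label dose unless dosing began on the 1st. For subjects randomized to control, the event then leaves the open-label treatment-emergent and Safety-HMTM tables. It appears in the control arm's double-blind tables only if those are re-run on final data, which SAP 1.6 leaves optional.

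Two stronger readings are tempting and do not hold:

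- That every switch-month event with a missing day is moved. Dates settled in the manual review are not, and an event recorded as worsening after the open-label dose still qualifies.
- That all HMTM safety tables are biased in the drug's favour. Early starters' events only move from the open-label to the double-blind HMTM period; they stay in the Safety-HMTM analysis and raise the double-blind HMTM counts.

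The number of affected events is unknown and probably small. The 48% rests on uniform start days and uniform onset, and the 2% to 10% missing shares are illustrations without a source in the documents. The point is worth correcting because the error is systematic and cheap to remove, not because it is shown to be large.

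**What to change.** Add to SAP 4.2, under start dates:

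> For subjects who entered the open-label phase, an adverse event whose partial start date falls in the same month and year as the first open-label dose (or, with the month missing, in the same year) is imputed to that dose date, unless the stop date, the visit at which the event was recorded (including the Visit 7 pre-dose adverse event review) or an earlier report shows an earlier onset.

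Also repeat the partial-date review at the open-label data review meeting, so that imputation remains the fallback.

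The work is one sentence, a small derivation change and one more review step. The statistical cost is larger than a handful of events: under uniform onset about half of the unresolved switch-month dates (48.4%, before the exceptions above) began before the switch and would count under HMTM, and possibly more for year-only dates. SAP 4.2 already accepts the same trade-off at first dosing. Imputed events would also fall on open-label day 1, so they should be flagged in the table of events starting that day.
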